518 dynamics and biological pathways within the human host that are affected by
519 military-relevant stress and are associated with physical and cognitive performance,
520 and identify novel markers of physiological stress.

521

522 **B5. RESEARCH PLAN**

523

524 **B5.1 Research Design**

525

526 This randomized cross-over study will consist of four sequential phases (SUSOPS 1, Recovery
527 1, SUSOPS 2, and Recovery 2).

528

529 **B5.2 Research Subjects/Population(s)**

530

531 **B5.2.1 Subject Population(s)**

532

533 Healthy, recreationally-active adult men, who are active duty military, will be recruited to
534 participate in this study. Male subjects were chosen because of known sex differences in
535 iron status and absorption and differences in their response to exercise, including the IL-
536 6 response to exercise [62, 63]. Pending the outcomes from this study, future, more
537 targeted studies will be designed to address potential sex-based differences in
538 physiological responses to SUSOPS.

539

540 **B5.2.2 Number of Subjects, Records, and/or Specimens**

541

542 This protocol requires 15 subjects complete testing to provide 80% power to detect
543 significant differences in circulating hepcidin responses between SUSOPS 1 and
544 SUSOPS 2. Up to 60 subjects will be enrolled to account for attrition and screening

545 failures in order to get complete data on 15 subjects. See section B5.8.1 for details on
546 sample size calculations.
547

548 **B5.2.3 Inclusion Criteria**

- 549 • Men who are active duty military, aged 18 – 39 years
- 550 • Weight stable in the past 2 months (\pm 2.27 kg)
- 551 • Healthy without evidence of chronic illness, medication use, or musculoskeletal injury
- 552 as determined by the USARIEM Office of Medical Support and Oversight (OMSO)
- 553 • Recreationally active (2-4 days per week aerobic and/or resistance exercise)
- 554 • Refrain from taking any pain-relievers (e.g., acetaminophen), nonsteroidal anti-
- 555 inflammatory drugs (e.g., aspirin, Advil®, Aleve®, Naprosyn®), or any other aspirin-
- 556 containing product for 10 days before starting and at least 5 days after completing
- 557 the study
- 558 • Refrain from the use of alcohol and nicotine for the duration of the study
- 559 • Willing to refrain from alcohol, smoking any nicotine product (includes e-cigarettes),
- 560 vaping, chewing tobacco, caffeine, and dietary supplement use, and from

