We have previously shown that an increase of intestinal permeability of 55-60% is associated with inflammation in military-relevant environments (USARIEM protocol 14-33HC [44]). Using means (pre-SUSOPS sucralose excretion = 2.0%), standard deviations (SD = 1.1), and correlations for repeated measurements of sucralose excretion (r = 0.5) from 14-33HC, we estimate that 14 subjects will allow detection of a main effect of study phase (BL vs. SUSOPS-NEG BAL vs. SUSOPS-BAL) if the effect size of SUSOPS-BAL vs. SUSOPS-NEG BAL on intestinal permeability is medium (~20% decrease) at power = 0.80 and alpha = 0.017 (<https://glimmpse.samplesizeshop.org/>). Of note, larger effect sizes have been reported in studies investigating the effects of nutritional interventions on intestinal permeability during exercise [105]. Additionally, we feel that it is likely that the SDs measured in this laboratory study will be slightly lower than those measured in our previous study (14-33HC) which was conducted in a field environment. A 25% decrease in the SD would allow us to detect a main effect of phase with 11 subjects at power = 0.80 and alpha = 0.017. As such we expect an n of 11 to 15 will provide adequate power to detect a main effect of phase on intestinal permeability.

Power calculations for appetite-mediating hormones outcomes were conducted using data obtained during USARIEM protocol H10-09 [73, 106]. In that study an energy deficit (3700 kcal/d) slightly greater than that which will be imposed in this study resulted in a 2.5-fold decrease in fasted acyl ghrelin, a 2.2 fold decrease in leptin, a 1.7-fold decrease in PYY, and a 3-fold increase in PP concentrations concomitant to an ~11-fold increase in appetite and overeating during recovery from energy deficit. Based on these results we expect to observe the hormone responses in the table below where fasting concentrations will be approximately maintained during BAL, and the maximal difference between BAL and NEG BAL will be observed on SUSOPS day 3 followed by a full recovery of hormone concentrations by recovery day 3. For all but PP, 12 subjects will provide ≥80% power at alpha = 0.01 to detect a phase-by-time interaction.

	BAL				NEG BAL				SD	r	n
	S-d1	S-d3	R-d1	R-d3	S-d1	S-d3	R-d1	R-d3			
Ghrelin	185	185	185	185	185	75	135	185	90	P,0.65; T, 0.60	11
Leptin	9	9	9	9	9	4.1	6.5	9	5	P,0.60; T, 0.75	11
PYY	170	170	170	170	170	100	135	170	170	P,0.85; T, 0.85	12
PP	65	65	65	65	65	195	130	65	100	P,0.30; T, 0.30	19

1425

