1426
1427
1428
1429
1430
1431
1432
1433
1434

Samples sizes (n) calculated using <https://glimmpse.samplesizeshop.org/>. r, correlation between phases (P) and over time within each phase (T); R, recovery; S, SUSOPS; SD, standard deviation. Values based on those measured during USARIEM protocol H10-09 [109]].

Using data obtained using the SmartPill in a study of 73 healthy adults we estimate that mean gastrointestinal transit time at baseline will be 29.5 hr (SD = 11.0 hr) [107]. Horner et al. [108] reported a large effect size of 1.0 in a meta-analysis of high-quality studies that measured changes in orocecal transit time in response to exercise. A similar effect size was reported by Corvilain et al. [109] who measured gastric emptying in healthy

1435 adults before and after a 4-d fast. Using these data and a conservative correlation
1436 between repeated measurements of $r = 0.50$ (Diaz-Tartera et al. [107] reported $r = 0.99$),
1437 we estimate that $n = 8$ participants will provide $>80\%$ power to detect a main effect of
1438 condition at $\alpha = 0.05$. This sample size will also provide $>80\%$ power to detect a
1439 main effect should the effect size be medium (effect size = 0.5) and the correlation
1440 between repeated measurements ($r = 0.90$) more similar to that reported by Diaz-Tartera
1441 et al. [107]. We will enroll at least $n = 9$ in this procedure to ensure complete data is
1442 collected on 8 participants. Due to equipment availability, $n = 9$ is also the maximum
1443 number of participants we can measure simultaneously. However, should multiple
1444 iterations be needed to complete data collection, we will enroll up to $n = 9$ participants
1445 during each iteration. Although $n = 8$ is sufficient to detect a main effect of condition,
1446 enrolling more than $n = 9$ will provide greater power to detect associations between
1447 changes in gastrointestinal transit time and changes in gut microbiota composition,
1448 intestinal permeability, and appetite-related outcomes.

1449
1450 Next Generation Sequencing (maximum 200 million pair-end reads) of blood mRNA
1451 samples from 15 participants will yield 60% statistical power to detect a true difference in
1452 expression of at least 1.5 fold with group coefficient variation 0.4, and a conservative
1453 false discovery rate of 0.05 using moderated t -tests and with transcriptome coverage of
1454 9 over reference human genome with sequence length of 150 base pairs. Note, a more

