1455 liberal false discovery rate (e.g., 0.20) may be used to reduce type 2 error rates and
1456 increase power. For microbiome analysis, shotgun sequencing (maximum 50 million
1457 pair end reads) of 15 participants will achieve $\geq 69\%$ power to detect a true difference in
1458 relative abundance of at least 1.5 fold with group coefficient variation 1.3, and false
1459 discovery rate of 0.05. Again, a more liberal false discovery rate (e.g., 0.20) may be
1460 used to reduce type 2 error rates and increase power. Power calculations were
1461 conducted using pairwise distances and PERMANOVA power with respect to effect size.
1462 However, power will be enhanced by correlating the blood mRNA data with other omics
1463 readouts derived from saliva (microRNA-seq, metabolomics and microbiome) and blood
1464 (targeted microRNA and metabolomics), and by temporal sample collection. As such,
1465 we expect that 15 participants will provide adequate power to detect differences in blood
1466 mRNA expression, and gut microbiome community and genome composition between
1467 study phases, and correlations between these parameters and other –omics readouts.

1468 **B5.8.2 Data analysis**

1469
1470
1471 Statistical analyses will be conducted using either SPSS (IBM Corp. Armonk, NY), SAS
1472 9.3 (SAS Institute Inc., Cary, NC), or equivalent. Common descriptive statistics will be
1473 used to describe volunteer characteristics. Shapiro-Wilk tests will be used to determine
1474 normality of data, and transformations will be applied as appropriate to ensure model
1475 assumptions are met. Correlation and multiple regression will be used to evaluate
1476 relationships between study outcomes.

1477 **Primary Objectives**

1478
1479 Linear mixed models will be used to determine main effects of phase (SUSOPS BAL and
1480 SUSOPS NEG BAL), time within phase, and their interaction on inflammation, iron
1481 absorption, mood/cognitive, and measures of muscle, nutritional, and metabolic
1482 homeostasis. If phase by time interactions are observed, a Bonferroni correction will be
1483 applied for multiple comparisons. Statistical significance will be set at $P < 0.05$. To test
1484 for carryover effects a main effect of group (SUSOPS BAL first, SUSOPS NEG BAL first)

1485 and a group-by-phase interaction will be included in initial models. These terms will be
1486 removed if they do not significantly contribute to the overall fit of the model. When

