1518 macronutrient proportion and energy intake). Models will include subject as a random
1519 factor, and study phase, time within phase, and their interaction as fixed factors.
1520 Separate analysis will be conducted for fasted and post-exercise appetite-mediating
1521 hormones. To test for carryover effects a main effect of group (SUSOPS BAL first,
1522 SUSOPS NEG BAL first) and a group-by-phase interaction will be included in initial
1523 models. These terms will be removed if they do not significantly contribute to the overall
1524 fit of the model. When significant phase-by-time interactions are observed post hoc
1525 comparisons will be made using paired t-tests with Bonferroni corrections.

1526

1527 The mRNA seq strand-specific libraries will be assayed using the Illumina HiSeq
1528 platform. Paired end reads of the strand-specific RNA sequences (RNA-Seq) will be
1529 generated using NextSQ from one flow cell with eight lanes, producing at least 30 million
1530 reads of 100 bases per sample. Based calling and expression analysis will be conducted
1531 using the Illumina-provided tool CASAVA. miRNA (20-40 bp) will be size selected from
1532 total RNA and will be processed by Illumina NextSQ. Image analysis and base calling
1533 will be performed using the newest available version of the Illumina pipeline.

1534 Preprocessing of raw base calls and sample de-multiplexing will be performed using the

1535 standard open source tool CASAVA. The microRNA read count matrix will be generated
1536 by a series of tool kits of latest version including CutAdapt, short read aligner Bowtie and
1537 PICARD. Metabolomics and proteomics reads will be processed by the software offered
1538 by the vendors namely Waters Corporation and BioRad, respectively.
1539

1540 Using a systems approach, we will integrate multiple levels of biological information. We
1541 have published the analysis pipeline and implemented it successfully in the past. Our
1542 pipeline uses industry standards and our established SOPs. We will start by analyzing
1543 and processing data at the analyte level for each data type such as mRNA expression,
1544 miRNA expression, microbiome, proteomics, and metabolomics. We will first examine
1545 the confounding factors or batch effects caused by non-biological factors, such as the
1546 technical error, sample processing date etc., using principal component analysis and

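### The fasted appetite-hormone models name subject as their only random term, although they were sized with two separate correlations; fitted literally, the phase test rejects a true null in about 13–28% of trials at nominal 5%

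*Combined protocol and SAP*

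**What the plan says.** In B5.8.2, Secondary Objectives, the paragraph on appetite hormones, appetite ratings and food choice ends its outcome list and then states the model: "macronutrient proportion and energy intake). Models will include subject as a random" "factor, and study phase, time within phase, and their interaction as fixed factors". It names no further random term and no residual covariance. It adds "Separate analysis will be conducted for fasted and post-exercise appetite-mediating" hormones. By the sampling days in B5.3, that means four fasted draws per phase and two post-exercise draws per phase. Table 1 marks a single leptin draw on the exercise days.

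Follow-up testing depends on the interaction: "fit of the model. When significant phase-by-time interactions are observed post hoc" comparisons are made with Bonferroni-corrected paired t-tests. The opening of B5.8.2 also allows transformation: "normality of data, and transformations will be applied as appropriate to ensure model" assumptions are met.

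B5.8.1 sizes four of these hormones. It claims that, for all but PP, 12 subjects give at least 80% "power at alpha = 0.01 to detect a phase-by-time interaction". The footnote to its table defines r as "correlation between phases (P) and over time within each phase (T"). B5.2.2 sets the number of completers: "This protocol requires 15 subjects complete testing to provide 80% power to detect" the hepcidin difference.

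**The concern.** A random intercept for subject with independent residuals implies one common correlation among all eight fasted values from a person. The sizing table assumes two correlations, and P and T differ for ghrelin and leptin. Even where they are equal (PYY, PP), values that differ in both phase and time are less correlated than either figure. A single pooled residual then serves as the error term for phase, time and interaction, whose true error variances differ.

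Two things are at stake. The BAL versus NEG BAL main effect, and any interval reported for it, would look more precise than it is. The phase-by-time test, which is the one that was sized, would be measured against too large an error and would lose the planned power.

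**Working it through.** **Inputs** (B5.8.1 hormone table; d is BAL minus NEG BAL at S-d1, S-d3, R-d1, R-d3):

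| | SD | d | P | T | stated n |
|---|---|---|---|---|---|
| Ghrelin | 90 | 0, 110, 50, 0 | 0.65 | 0.60 | 11 |
| Leptin | 5 | 0, 4.9, 2.5, 0 | 0.60 | 0.75 | 11 |
| PYY | 170 | 0, 70, 35, 0 | 0.85 | 0.85 | 12 |
| PP | 100 | 0, −130, −65, 0 | 0.30 | 0.30 | 19 |

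**1. Reproduce the plan's n.** The plan does not print the correlation between values that differ in both phase and time; take it as P×T. Each orthonormal time contrast of the phase difference then has variance 2·SD²(1−P)(1−T). The noncentrality per subject is Σ(d−d̄)² / [2·SD²(1−P)(1−T)]:

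- Ghrelin: 8200 / (2·8100·0.14) = 3.62
- Leptin: 16.57 / (2·25·0.10) = 3.31
- PYY: 3368.75 / (2·28900·0.0225) = 2.59
- PP: 11618.75 / (2·10000·0.49) = 1.19

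With a multivariate test on F(3, n−3) at alpha 0.01, the smallest n reaching 80% is **11, 11, 12, 19**, exactly as stated. The other readings tried do not match. A univariate test gives 7, 7, 8, 15. A cross-phase correlation of P at every pair of times gives 19, 18, 46, 25 (multivariate) or 15, 14, 42, 21 (univariate). The P×T structure is therefore well supported as the plan's own.

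**2. Error variances, fasted models** (units of SD²). Phase: (1−P)(1+3T), 1 df. Time: (1+P)(1−T), 3 df. Interaction: (1−P)(1−T), 3 df. The random-intercept fit uses their pooled mean, (phase + 3·time + 3·interaction)/7.

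| | phase | time | interaction | pooled | phase ÷ pooled | pooled ÷ interaction |
|---|---|---|---|---|---|---|
| Ghrelin | 0.980 | 0.660 | 0.140 | 0.483 | 2.03 | 3.4 |
| Leptin | 1.300 | 0.400 | 0.100 | 0.400 | 3.25 | 4.0 |
| PYY | 0.533 | 0.278 | 0.023 | 0.205 | 2.60 | 9.1 |
| PP | 1.330 | 0.910 | 0.490 | 0.790 | 1.68 | 1.6 |

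**3. Phase type I error at 0.05.** To a close approximation it is 2Φ(−1.96/√ratio), with critical values 1.96/√2.03 = 1.38, 1.96/√3.25 = 1.09, 1.96/√2.60 = 1.22 and 1.96/√1.68 = 1.51. That gives **17%, 28%, 22% and 13%**. Simulation of 40,000 balanced trials per setting agrees at n = 12 and n = 15, so more subjects do not help. Coverage of a nominal 95% interval is the complement: about 83%, 72%, 78% and 87%. On a log scale (assumed lognormal, constant coefficient of variation) the error is 17%, 27–28%, 22–23% and 13–17%.

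**4. Post-exercise models.** With two times and the same P and T, the variances are (1−P)(1+T), (1+P)(1−T) and (1−P)(1−T), 1 df each.

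- Ghrelin: 0.560 / [(0.560+0.660+0.140)/3] = 1.24, error about 8%
- PYY: 0.2775 / [(0.2775+0.2775+0.0225)/3] = 1.44, error about 10%
- PP: 0.91 / [(0.91+0.91+0.49)/3] = 1.18, error about 7%

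**5. Phase-by-time test, fasted models fitted as written.** Type I error at 0.05 is below 1% for all four hormones. Simulated power on the raw scale:

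| | n=12, alpha 0.01, as written | n=12, alpha 0.01, sizing test | n=15, alpha 0.05, as written |
|---|---|---|---|
| Ghrelin | 60% | 94% | 98% |
| Leptin | 36% | 92% | 91% |
| PYY | under 1% | 82% | about 5% |
| PP (excluded from the 80% claim) | 36% | 39% | 80% |

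On the assumed log scale at n = 12 and alpha 0.01, ghrelin and leptin are at 98% or more and PYY at 11–33%. At n = 15 and alpha 0.05, PYY is at 81–98% and PP at 51–59%.

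**6. With three random intercepts.** Variance shares PT (subject), T(1−P) (subject-by-phase), P(1−T) (subject-by-time) and (1−P)(1−T) (residual) reproduce the structure in step 1. In balanced data, phase is tested on 1 and n−1 df and the interaction on 3 and 3(n−1) df. Both simulated type I errors are about 5% for all four hormones.

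**The case against.** The strongest reply is that the text is silent rather than wrong. It says the models include subject as a random factor, not that nothing else may be added, and B5.8.1 shows the authors had both correlations in mind. This stands in part: the inflation is conditional on a literal fit. But a random intercept with independent residuals is a natural reading of the sentence, and several richer structures would be defensible and give different p-values, so the choice belongs in the plan.

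Second, phase is neither the sized test nor the gate. This stands. A reader might infer that the plan's hormone conclusions carry a 13–28% false-positive rate. The documents do not support that: the gating interaction is conservative in the fasted models, and the paired t-tests do not use the pooled residual. B5.8.2 also does not specifically plan the interval whose coverage is given above.

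Third, the near-zero PYY power comes from a normal raw-scale model. With mean 170 or 100 and SD 170, such a model implies negative values 16% or 28% of the time, and B5.8.2 allows transformation. This also stands: the PYY figure is a worst case. At 15 completers and alpha 0.05, ghrelin and leptin remain well powered.

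Fourth, 13–28% cannot be carried over to the post-exercise models, where the same correlations give 7–10%. That is correct.

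**Conclusion.** The point holds for the fasted ghrelin, leptin, PYY and PP models. The stated random term does not match the covariance used to size them. Fitted literally, the phase test has about 17%, 28%, 22% and 13% type I error at nominal 0.05, and the interaction falls short of the stated 80% power at n = 12 and alpha 0.01 on the raw-scale inputs. The post-exercise models show the same fault more mildly.

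This rests on a literal fit with independent residuals, on the plan's P and T, on the P×T entry supported by exact reproduction of all four sample sizes, and on balanced data. The 0.05 level is the one stated under Primary Objectives; no separate level is given for hormones.

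It may be tempting to extend this to IL-6, hepcidin and iron absorption, or to the other secondary models. The plan gives no P and T for those, so no such claim is made. The outcomes are secondary and the change is small: it should be made, but it does not threaten the trial's main question.

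**What to change.** In the appetite-hormone models of B5.8.2, replace the single subject term with: *Random intercepts will be fitted for subject, subject-by-phase and subject-by-time, with Kenward–Roger degrees of freedom.* All three are needed. Adding subject-by-phase alone corrects the phase test but leaves the interaction conservative (type I error at most 1.3%, and raw-scale PYY power of 1% at n = 12 and alpha 0.01).

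The cost is one sentence and a slightly larger model. If all of a person's values really are equally correlated, some phase power is lost: with common correlation 0.6, n = 15, a phase difference of 0.3 SD and alpha 0.05, it falls from 73% to 68%. In the two-time models a variance component may sometimes be estimated at zero, so the plan should say what is done then.

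The return to about 5% was checked in balanced data only. B5.8.1 cites about 30% attrition in an earlier study, and C3 allows data up to withdrawal to be used, so the sponsor should confirm the behaviour with incomplete subjects.

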1487 significant phase-by-time interactions are observed post hoc comparisons will be made
1488 using paired t-tests with Bonferroni corrections.

1489

1490 **Secondary Objectives**

1491 Linear mixed models will be used to examine changes in intestinal permeability and
1492 gastrointestinal transit time. Models will include subject as a random factor, and study
1493 phase as a fixed factor. To test for carryover effects a main effect of group (SUSOPS
1494 BAL first, SUSOPS NEG BAL first) and a group-by-phase interaction will be included in
1495 initial models. These terms will be removed if they do not significantly contribute to the
1496 overall fit of the model. When a significant main effect is observed post hoc
1497 comparisons will be made using paired t-tests with Bonferroni corrections.

1498

1499 Fecal metabolomics data will be visualized using hierarchical average-linkage clustering
1500 and principal components analysis. Bacterial taxonomic data will be visualized using
1501 hierarchical average-linkage clustering and principal coordinates analysis of beta (i.e.,
1502 between samples) diversity scores (e.g., Bray-Curtis, and weighted and unweighted
1503 UniFrac). Alpha (i.e., within-sample) diversity will be calculated for taxonomic data using
1504 Shannon, Simpson and Chao1 indices. Linear mixed models will be used to examine
1505 changes in biomarkers of gut health, fecal metabolite concentrations, and alpha diversity
1506 over time. Models will include subject as a random factor, and study phase, time within
1507 phase, and their interaction as fixed factors. To test for carryover effects a main effect of
1508 group (SUSOPS BAL first, SUSOPS NEG BAL first) and a group-by-phase interaction
1509 will be included in initial models. These terms will be removed if they do not significantly
1510 contribute to the overall fit of the model. Models for bacterial taxa and gene abundance
1511 will be analyzed using the R statistical software package “DESeq2” or equivalent. The
1512 Benjamini-Hochberg correction will be used to control the false discovery rate in
1513 microbiome-specific and metabolite models. Data analysis will be completed using
1514 SPSS, XLSTAT, R, Qiime, or similar software as needed.

1515

1516 Linear mixed models will be used to examine changes in appetite-mediating hormone
1517 concentrations, appetite ratings, food preferences, food choice during recovery (i.e., diet

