1547 ANOVA. If necessary, corrections will be made using the COMBAT algorithm. All
1548 datasets will be visually inspected using PCA, heatmaps, and boxplots before and after
1549 any required normalization, correction, or filtering, to assure quality control.
1550

1551 Using R package the significantly altered analytes will be mined by t-test p-values
1552 (<0.05) and fold-change 1.5. The R package BETR in conjunction with standard and
1553 lagged correlation analysis will be used to find biological signatures which vary
1554 systematically with the phenotypic data. Data dimension reduction, specifically latent
1555 factor analysis for phenotypic (clinical indices of disease onset) and PCA/PCoA for
1556 omics data will be used to uncover underlying mechanisms and dominating trends. Venn
1557 diagrams will be used to identify the biological signatures, including the molecules and
1558 enriched networks/pathways, which will emerge common/unique to different treatment
1559 groups and common/unique to control vs. treated specimens. To assess gene ontology
1560 and pathway enrichments, and analyze regulatory networks and common pathways we
1561 will use the Hypergeometric Test (false discovery rate, $q < 0.05$) of Bingo 2.44 and
1562 ClueGO (Cytoscape 3.0.1 plugins; <http://www.cytoscape.org/>), Fisher's Exact Test of
1563 Ingenuity Pathway Analysis (IPA, Ingenuity, Inc., Redwood, CA), and Gene Set
1564 Enrichment Analysis (<http://www.broadinstitute.org/gsea/index.jsp>) software sets. Gene-
1565 metabolite condition 'interactomes' will be constructed and visualized using Gephi.0.8.2
1566 beta (www.gephi.org). Using a suite of platforms such as ClueGo, Bingo, IPA, David and
1567 IMPaLA, we will deliver a panel of networks informed by multiple levels of molecular
1568 evidence that are unique to treatment groups. From these analyses we will produce a
1569 suite of networks informed by multiple levels of molecular evidence that are unique to
1570 treatment groups.
1571

1572 We will employ our in-house developed tool, Core Module Biomarker Identification with
1573 Network Exploration (COMBINER), to look for those novel functional groupings of
1574 molecules, which are statistically perturbed across time course. In addition, Feature
1575 Assisted Clustering for Time-series (FACT), a pipeline for exploratory analysis and
1576 visualization of longitudinal data, will identify differential expressed molecules,

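### The rule for calling an mRNA, miRNA or protein altered (t-test P<0.05 plus an observed 1.5-fold change) has no list-wide correction and is not the FDR 0.05 rule on which the mRNA power rests

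*Combined protocol and SAP*

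**What the plan says.** The systems-biology part of B5.8.2 (Secondary Objectives) begins with analyte-level work on mRNA, miRNA, microbiome, proteomic and metabolomic data. It then gives the selection rule: "Using R package the significantly altered analytes will be mined by t-test p-values" (cut-off 0.05) and a fold-change of 1.5. It does not say whether the t-test is paired and names no adjustment across analytes. The q<0.05 later in the same paragraph applies to ontology and pathway enrichment terms.

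Earlier in B5.8.2, the "Benjamini-Hochberg correction will be used to control the false discovery rate in" microbiome-specific and metabolite models. mRNA, miRNA and proteins are not mentioned there.

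B5.8.1 justifies the sequencing sample differently: "samples from 15 participants will yield 60% statistical power to detect a true difference in" "expression of at least 1.5 fold with group coefficient variation 0.4, and a conservative" "false discovery rate of 0.05 using moderated" t-tests, "and with transcriptome coverage of" 9. It adds that a more "liberal false discovery rate (e.g., 0.20) may be used to reduce type 2 error rates and" raise power. For the microbiome it assumes a "relative abundance of at least 1.5 fold with group coefficient variation 1.3, and false" discovery rate 0.05.

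**The concern.** The power statement and the analysis rule differ in two ways. The test is moderated in one and an unqualified t-test in the other. The error criterion is an FDR across the list in one and a P-value per analyte in the other. The optional 0.20 is still an FDR, so it does not close the gap.

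Under the selection rule as written, the expected share of false entries in an mRNA, miRNA or protein list is not fixed in advance. It depends on how variable each analyte is, because only the fold-change filter stands between a 5% per-test error and the list. The power figure also does not tell the reader what the stated rule can find. For microbiome and metabolite analytes, B5.8.2 contains two rules and does not say which governs the integration step.

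At stake is how the analyte lists under Secondary Objective 5 are read, and whether the threshold could be chosen after the results are seen.

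**Working it through.** **Inputs from the plan.** n=15; true change 1.5-fold, ln 1.5 = 0.4055; mRNA CV 0.4; coverage 9; FDR 0.05; selection at P<0.05 and 1.5-fold; microbiome CV 1.3; 65 salivary proteins (B5.4, Saliva analysis).

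**Assumptions, not in the plan.** Paired two-sided t-test on the log scale; within-person correlation r = 0.5, 0.25 or 0; 20,000 transcripts; share of nulls π0 = 0.80, 0.90 or 0.95; every non-null transcript changed by exactly 1.5-fold; one contrast.

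**The plan's 60%.** The usual normal approximation with two independent groups and a per-test two-sided α of 0.05 gives Φ(0.4055/√(2(1/9+0.16)/15) − 1.960) = Φ(2.133 − 1.960) = 56.9%. That is near 60%, but it is not an FDR calculation. With a paired log-difference variance of 1/9+0.16 = 0.271, FDR 0.05 gives 65%, 52% and 40% at π0 = 0.80, 0.90 and 0.95, and 60% at a π0 of about 0.85. The plan gives neither π0 nor the correlation, so the 60% is neither confirmed nor refuted.

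**SD of the paired log difference.**
- CV 0.4 alone: √(2(1−r) ln 1.16) = 0.385, 0.472, 0.545 for r = 0.5, 0.25, 0.
- With counting noise at coverage 9: √(2[(1−r)0.16 + 1/9]) = 0.618, 0.680, 0.736. Here r applies to the biological part only, because counting noise is independent between samples.

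**Performance of the stated rule.** An analyte passes if |t| exceeds the 5% limit on 14 degrees of freedom and |mean log difference| > 0.4055. Probabilities come from integrating over the chi-square(14) distribution of the sample variance. Realised FDR = π0·null/(π0·null + (1−π0)·power). The false-call column is the count if all 20,000 transcripts were null.

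| Noise model | SD | Null pass | False calls per 20,000 | Power at true 1.5-fold | FDR at π0 0.80 / 0.90 / 0.95 |
|---|---|---|---|---|---|
| CV 0.4 | 0.385 | 0.000046 | 0.9 | 50.0% | 0.04% / 0.08% / 0.17% |
| CV 0.4 | 0.472 | 0.00087 | 17 | 50.0% | 0.7% / 1.6% / 3.2% |
| CV 0.4 | 0.545 | 0.0039 | 78 | 49.8% | 3.0% / 6.6% / 13% |
| + coverage 9 | 0.618 | 0.0104 | 209 | 48.8% | 8% / 16% / 29% |
| + coverage 9 | 0.680 | 0.0181 | 361 | 46.9% | 13% / 26% / 42% |
| + coverage 9 | 0.736 | 0.0255 | 510 | 44.4% | 19% / 34% / 52% |

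**The 50% ceiling.** If the true change equals the cut-off, a roughly symmetric estimate falls above it about half the time at any n, and the P-value condition can only lower that. The rule reaches 60% at a true change of 1.54- to 1.56-fold (CV 0.4 alone) or 1.57- to 1.62-fold (with coverage 9).

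**Other layers.** For 65 null proteins, P<0.05 alone gives 65 × 0.05 = 3.25 expected false calls; the fold filter can only reduce this. If the selection rule also governed taxa at CV 1.3, the SDs would be √(2(1−r) ln 2.69) = 0.995 to 1.407 and 4.6%-5.0% of null taxa would pass, so the filter would remove almost nothing. No text says that it does govern them.

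**Power under Benjamini-Hochberg FDR 0.05 at a true 1.5-fold change.** Solve a = 0.05[π0·a + (1−π0)·power(a)] for the per-test level a. Across the same r and π0:
- CV 0.4 alone: 6%-83% (ordinary paired t) and 33%-93% (variance treated as known, the limit of full moderation).
- With coverage 9: 0%-14% and 4%-36%.

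**The case against.** The strongest reply is that this is discovery work. The plan's verb is mining, the objective is the last of five secondary ones, enrichment has its own q<0.05, and BETR, COMBINER and FACT are also planned. B5.8.1 does mention an FDR for mRNA, a moderated t-test is still a t-test, and the text refers to a published pipeline and in-house procedures that may hold the detail. For low-variance analytes the fold filter works well: at CV 0.4 alone, realised FDR is below 5% in 7 of the 9 scenarios. An FDR rule can also cost power.

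Much of this stands, and it is why the point is minor. It does not remove the inconsistency. The only selection rule written for single analytes carries no list-wide control, the enrichment q-value adjusts across terms and not across the analytes that enter the list, and the plan calls the results significant and not exploratory.

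Three stronger readings are tempting, and the documents support none of them:
- A reader might infer that no omics layer has FDR control. B5.8.2 plans Benjamini-Hochberg for microbiome and metabolite models, so the defect there is two unreconciled rules.
- A reader might infer that the 60% is wrong. It was stated for another rule and for differences of at least 1.5-fold, and it is attainable under some inputs. The 50% ceiling follows from the mismatch and is not a second error.
- A reader might infer that the lists will be mostly false. Only one of the 18 scenarios exceeds 50%.

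**Conclusion.** The point holds as a consistency defect for mRNA, miRNA and protein analytes: the stated selection rule is not the powered rule and fixes FDR at no level. For microbiome and metabolite analytes the plan must say which of its two rules applies.

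The textual mismatch is certain. Its size is not: realised FDR is 0.04%-13% at CV 0.4 alone and 8%-52% with coverage-9 noise, with about 1-78 and 209-510 false calls per 20,000 null transcripts. These ranges rest on the assumed correlation, share of nulls, list size and noise model. The ceiling of about 50% at exactly 1.5-fold needs only a roughly symmetric estimate.

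Severity is minor. The primary IL-6, hepcidin and iron analyses are untouched. So is n=15, which B5.2.2 ties to hepcidin.

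**What to change.** State one rule in B5.8.2, in either of two ways.

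(a) For mRNA, miRNA and proteins, use subject-blocked moderated tests with Benjamini-Hochberg FDR 0.05 within each omics layer and contrast. Keep the models and correction already planned for microbiome and metabolite data, and say that they also govern the integration step. Report fold change descriptively, and label any FDR 0.20 list exploratory.

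(b) Keep the P<0.05 plus 1.5-fold list, drop the word *significantly*, label the list exploratory and print Benjamini-Hochberg q-values beside it.

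In both cases recompute the mRNA power for the rule kept and state its inputs: within-person correlation, share of transcripts altered and coverage. If the observed 1.5-fold filter stays, give power as at most about 50% at a true 1.5-fold change.

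The work is one paragraph and one power statement, with no new data or subjects. Option (a) may shorten the lists: with coverage-9 noise its power at a true 1.5-fold change (at most 14% with an ordinary t-test, 36% with full moderation) is below the present rule's 44%-49% in every scenario. Option (b) costs essentially nothing.
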